## LIST OF ABBREVIATIONS

AE	Adverse Event/Adverse Experience
ASES	American Shoulder Elbow Society
CFR	Code of Federal Regulations
CRF	Case Report Form
FDA	Food and Drug Administration
GCP	Good Clinical Practice
HIPAA	Health Insurance Portability and Accountability Act
INB	Interscalene Nerve Block
IRB	Institutional Review Board
PHI	Protected Health Information
PI	Principal Investigator
PROMs	Patient Reported Outcome Measures
SANE	Single Assessment Numeric Evaluation
SST	Simple Shoulder Test
VR-12	Veteran RAND 12 Item Health Survey

## Introduction

This document is a protocol for a human research study which will be evaluating the effect of liposomal bupivacaine INB on post-operative pain and narcotic consumption in patients undergoing primary total shoulder arthroplasty. This study will be carried out in accordance with the applicable United States government regulations and Mayo Clinic research policies and procedures.

### 1.1 Background

The “Opioid Crisis” has been characterized by a significant rise in the prevalence of opioid dependence and drug related deaths. Not only has this placed a substantial strain on the health care economy, but resultant government legislation has led to greater restrictions on narcotic prescriptions. Consequently, there has been increasing interest in the development of multi-modal pain control regimens, particularly, in the post-operative period.

Furthermore, in those patients undergoing orthopedic surgery, adequate pain control is highly important. Patients with poor post-operative pain management in the first 48 hours have an approximate 50 percent chance of achieving long-term satisfactory pain relief. Inadequate pain management has been shown to not only increase hospital length of stay, but increase the risk of thromboembolic events, pulmonary complications, and chronic pain. Regional analgesia through the use of local anesthetic agents is a commonly employed strategy for pain management. In shoulder surgery, specifically, peripheral nerve block with long acting local anesthetic is a well-established technique for pain control. Typical agents including bupivacaine and ropivacaine, in general, provide a block duration of 12 to 24 hours.

In 2011, liposomal bupivacaine (Exparel, Pacira Pharmaceuticals, San Diego, USA) was approved by the US Food and Drug Administration (FDA) for use as a local anesthetic for surgical site infiltration. Liposomal bupivacaine is composed of a phospholipid bilayer that encapsulates bupivacaine, extending drug delivery for up to 72 hours and potentially extending periods of regional analgesia. Early studies evaluating liposomal bupivacaine noted lower subjective pain scores, increased time to first opiate medication, and decreased opiate requirements when compared to placebo.

Liposomal bupivacaine was FDA-approved for use in interscalene nerve blocks (INB) in the setting of shoulder surgery on April 6, 2018. Despite approval, there is limited data comparing liposomal bupivacaine to traditional agents in this population. The objective of this study is to determine if peripheral nerve block with liposomal bupivacaine in combination with standard bupivacaine will prolong the duration of block, improve pain scores, and decrease opioid utilization in the post-operative period when compared to peripheral nerve block with standard bupivacaine alone.

### 1.2 Dose Rationale

The FDA approved dosing of liposomal bupivacaine for peripheral nerve block will be utilized (maximum dose of 133 mg). FDA approved dosing ratio of liposomal bupivacaine to

bupivacaine HCl will be utilized, which recommends mg dose of bupivacaine HCl to liposomal not to exceed 1:2.

### 1.3 Risks and Benefits

The most significant risks associated with this study are directly related to surgery itself.

Risks associated with the nerve block: Block failure, nerve injury, hematoma, infection, and pneumothorax

Serious risks associated with bupivacaine-containing products, while extremely rare, include:

1. *Central nervous system reactions*: persistent anesthesia and paresthesias, excitation and/or depression
2. *Cardiovascular reactions*: dysrhythmias, death
3. *Allergic reactions*: anaphylaxis, angioedema.

Patients who are at highest risk of these complications including patients with severe liver and respiratory disease will be excluded from this study.

Potential benefits from participation in the study include improved post-operative outcomes: diminished post-operative pain, and decreased opioid consumption.

## 2 Study Objectives

The primary outcome measure will be:

1. Mean difference in patient pain scores over the first 72 hours post-operatively between two groups

Secondary outcomes will include:

1. Total opioid consumption (as measured utilizing morphine intravenous equivalents) in first 72 hours and at 3 weeks
2. Patient perceived duration of block determined as the time patient perceives complete resolution of block
3. Patient satisfaction with pain control at 72 hours, 3 weeks post-operatively and patient reported outcome measures (SANE, SST, ASES, VR-12) at 3 weeks post-operatively

## 3 Study Design

### 3.1 General Description

This will be a prospective, single-blinded randomized clinical trial comparing outcomes in patients undergoing total shoulder arthroplasty (anatomic and reverse) who receive a peripheral

[figure not shown]
nerve block with liposomal bupivacaine in combination with standard bupivacaine versus standard bupivacaine alone. Subjects will be screened in the outpatient clinic upon initial patient election to proceed with shoulder replacement surgery. Interested and qualified patients meeting all inclusion criteria will be offered the opportunity to participate in this study. Once consent is obtained, baseline characteristics will be recorded and patients will be randomized to intervention or control. Following surgery, patients will be followed until their 3-week post-operative visit.

### 3.2 Number of Subjects

This study will require a sample size of 50 subjects per group in order to achieve 80% power. The target enrollment will be 110 total subjects in order to combat an expected attrition of 10%.

### 3.3 Duration of Participation

The duration of time that patients can expect to be directly involved in the study is 3-weeks; i.e. initial surgery up until the first post-operative visit at 3-weeks.

### 3.4 Primary Safety Endpoints

All patients will be continuously monitored for local anesthetic toxicity or other reaction to liposomal bupivacaine for the entire surgical scope of care. During surgery, standard ASA monitors will be in place. In the PACU, vital signs will be obtained every 15 minutes with continuous telemetry and pulse ox, with a minimum 2:1 RN monitoring. Continuous surveillance will be exercised for medication reaction or local anesthetic toxicity including but not limited to: tinnitus, perioral numbness, mental status changes, cardiac arrhythmia, respiratory compromise, rash, or hives. 20% intralipid for treatment of toxicity will be available at all times. In addition, patients will be monitored for signs of pneumothorax related to the peripheral nerve block including but not limited to: dyspnea, oxygen desaturation, or hemodynamic instability. At discharge, patients will be educated regarding signs and symptoms for local anesthetic toxicity and instructions to call the on-call physician with mild symptoms and present to the ED if moderate or severe symptoms.

## 4 Subject Selection Enrollment and Withdrawal

### 4.1 Inclusion Criteria

- All adult patients (>18 years of age)
- Patients undergoing standard or reverse total shoulder arthroplasty for the primary diagnoses of glenohumeral arthritis or cuff tear arthropathy
- Cognitively intact with the ability to give informed consent as outlined by our institutional review board.
- Patients must be capable of participating in the post-operative electronic survey and / or able to maintain a written diary of events

### 4.2 Exclusion Criteria

- Non-elective cases
- Infection, tumor, trauma
- Weight < 50 kg
- Patients with any contraindications to regional anesthesia including allergy or hypersensitivity to amide-type local anesthetics
- Patients with allergy to any component of medication regimen e.g. amide-type local anesthetics, oxycodone, hydromorphone, fentanyl
- Chronic pain patients with history of chronic opioid use (defined as 20 mg morphine equivalent / day for greater than 30 days pre-operatively)
- Concurrent painful physical condition that may require analgesic treatment that is not related to the shoulder surgery (chronic peripheral neuropathy, radiculopathy, or other neurologic disorder)
- Severe hepatic disease defined by clinical evidence of liver disease with abnormal liver function tests.
- Pregnancy

- Respiratory disease that contraindicates interscalene nerve block (elevated contralateral hemidiaphragm, contralateral pneumonectomy, or severe COPD with FEV1 < 50% predicted, and O2 dependence)

#### 4.3 Subject Recruitment, Enrollment and Screening

All patients >18 years of age who present to either the PI's ([name]) or Co-Investigator's ([name]) clinical practices for elective anatomic or reverse total shoulder arthroplasty for the primary diagnoses of glenohumeral arthritis or cuff tear arthropathy and meet the inclusion criteria will be invited to participate in the study.

#### 4.4 Early Withdrawal of Subjects

Should patient wish to withdraw from the study due to any major adverse events i.e. from the surgery, intervention, or the inpatient stay, he or she may do so without any penalty and we will monitor and treat any adverse event.

If patient decides he or she would like to withdraw from the study for any reason whatsoever, he or she may do so without any penalty even after data collection has begun.

### 5 Study Drug

#### 5.1 Description

Liposomal bupivacaine (Exparel, Pacira Pharmaceuticals, San Diego, USA) was approved by the US Food and Drug Administration (FDA) for use as a local anesthetic for surgical site infiltration. Liposomal bupivacaine is composed of a phospholipid bilayer that encapsulates bupivacaine, extending drug delivery for up to 72 hours and potentially extending periods of regional analgesia. It is administered in a liquid form. On April 6th, 2018 Exparel was FDA-approved for use in INB to produce postsurgical regional anesthesia.

In this study, liposomal bupivacaine will be utilized in peripheral nerve block for the purposes of postsurgical regional anesthesia in patients undergoing shoulder arthroplasty.

#### 5.2 Treatment Regimen

##### Liposomal Bupivacaine Group:

In this group, all INBs will be administered utilizing ultrasound guidance by an attending anesthesiologist experienced in the technique, or experienced anesthesiology resident with direct attending supervision and assistance. Study patients will receive 10ml (133 mg) of liposomal bupivacaine mixed with 7.5ml of 0.5% plain bupivacaine and 7.5ml of 0.25% bupivacaine. Further, 8 mg (2 ml) IV dexamethasone will be administered concomitantly at the time of the block

##### Control Group:

In this group, all peripheral nerve blocks will be performed with ultrasound guidance by an attending anesthesiologist experienced in the technique, or experienced anesthesiology

resident with direct attending supervision and assistance. Standard bupivacaine will be utilized. 25 ml of 0.5% bupivacaine for peripheral nerve block will be utilized. Further, 8 mg (2 ml) IV dexamethasone will be administered concomitantly at the time of the block.

### **5.3 Method for Assigning Subjects to Treatment Groups**

Our 110 participants will be equally randomized to one of two treatment arms using a randomized block strategy with varying block sizes. The randomization list will be created in SAS v9.4 (SAS Institute; Cary, NC) and will be uploaded into the REDCap randomization module.

The pharmacy team, the study coordinator, and the statistician will have access to the randomization module with the pharmacy team serving as the primary randomizers and the study coordinator and statistician serving as back-ups. Only the statistician will have knowledge of how the randomization list was built and will be the only one that has seen it.

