## **5.6 Masking/Blinding of Study**

Patients, care team in recovery, study team members collecting and recording data, and statisticians will be blinded to randomization assignment. The administering anesthesiologist and pharmacy will be unblinded. All patients will be documented in EMR as receiving liposomal bupivacaine to ensure the blind is maintained and to ensure that safety features in the EMR for all patients receiving liposomal bupivacaine are activated. Further, all additional standard precautionary measures (e.g. wrist band) will be similarly implemented for both patient groups.

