### 6.5 All Time Points

If patient non-compliance with electronic surveys is identified, the study coordinator will attempt to contact non-compliant patient to either encourage him/her to either complete the surveys, or to directly obtain respective data points from them. Further, patients who are given diaries will receive daily reminder phone calls from the study coordinator in the 72 hours following discharge.

Complications will be recorded. These include cardiac arrest, acute respiratory failure, venous thromboembolism event, ileus, SSI, deep infections, urinary tract infection, nerve injury, pneumothorax.

Schedule of Events				
Study Activity	Pre-op Visit	Surgical Stay	Time from discharge to first post-op visit	Post-op Visit
Study Agent Administration		X		
Informed consent	X			
Randomization		X a		
Demographics	X			
History / Physical Exam	X			
Concurrent Meds	X			
Pain Scores	X	X	X	X
PROMs b	X			X
Satisfaction Scores c			X	X
Opioid Use		X	X	X
Adverse Event Evaluation		X	X	

a: In pre-op, will be performed by pharmacy  
 b: ASES, SANE, SST, VR-12 scores  
 c: Obtained at 72 hrs post-op and at 1st post-op visit

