### **9.2 Source Documents**

The study coordinator will prepare and maintain adequate and accurate source documents designed to record all observations and other pertinent data for each subject. Source documents are defined as documentation of the observations and activities of a clinical study. Source documents may include, but are not limited to, study progress notes, e-mail, correspondence, subject quality of life surveys, subject diaries, computer printouts, laboratory data, and recorded data from automated instruments. All source documents for this study will be maintained by the

investigator in accordance with ICH GCP and applicable regional or national regulations. The official signed informed consent form (ICF) for each subject will be maintained as a source document, and a copy provided to the subject.

When paper source documents are used, ICH GCP and applicable regional or national regulations documentation guidelines will be followed. For example, incorrect entries should be crossed out with a single pen stroke. Corrections must be made adjacent to the item to be altered, initialed and dated with the reason for the correction if necessary by the investigator or designee. Overwriting of data or use of a liquid correction is not allowed.

Designated study personnel will enter data from source documents corresponding to a subject's visit into the protocol specific redcap database. Subjects will not be identified by name in the study database, but will be identified by a subject number.

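### The study coordinator can learn a patient's arm as back-up randomizer (5.3) and then collect that patient's missed pain scores (6.5), although 5.6 says data collectors are blinded; no safeguard is stated.

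*Combined protocol and SAP*

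**What the plan says.** Four sections of the combined protocol and SAP bear on the coordinator's role.

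- **5.3 (assignment):** "The pharmacy team, the study coordinator, and the statistician will have access to the randomization module". Pharmacy randomizes in the first instance; the coordinator and the statistician stand in as back-ups. The same section adds: "Only the statistician will have knowledge of how the randomization list was built and will be the only one that has seen it".
- **5.6 (masking):** "Patients, care team in recovery, study team members collecting and recording data, and statisticians will be blinded to randomization assignment". The next sentence gives the exceptions: "The administering anesthesiologist and pharmacy will be unblinded".
- **6.5 (all time points):** when surveys are missed, "the study coordinator will attempt to contact non-compliant patient", either to encourage completion "or to directly obtain respective data points from them". Diary patients also get daily reminder calls from the coordinator.
- **9.2 (source documents):** "The study coordinator will prepare and maintain adequate and accurate source documents designed to record all observations".

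Section 6.3 shows what the surveys hold: twice-daily home pain scores up to 72 hours after surgery. Section 2 makes pain over those 72 hours the primary outcome. Footnote a to the Schedule of Events in 6.5 assigns randomization to pharmacy and does not mention the coordinator.

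**The concern.** One role holds a route to the allocation and a duty to collect primary-outcome data. Someone who randomizes a patient would ordinarily see that patient's assignment. If the same person later asks that patient for a missed pain score, the score has been collected by someone who knows the arm, which 5.6 rules out.

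Pain is a subjective answer. A collector who knows the arm may, without intent, affect the answer or the effort spent on retrieving it. Retrieval matters in its own right here, because 7.2 carries the last observation forward: uneven chasing changes which values are observed and which are imputed. The exposed scores are those after discharge. Section 1.1 gives standard agents a block of 12 to 24 hours and liposomal delivery up to 72 hours, so much of any treatment difference would be expected in that later period. Masked arm codes at analysis would not repair scores already collected this way.

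**Working it through.** **Step 1. The roles side by side**

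| Section | Coordinator's position |
|---|---|
| 5.3 | Has module access; back-up randomizer |
| 6.5 | Contacts patients who miss surveys; may take the missing data from them |
| 9.2 | Prepares and maintains source documents |
| 5.6 | As a data collector, must be blinded; not among those declared unblinded |
| Schedule of Events, footnote a | Not mentioned; pharmacy randomizes |

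The sentence in 5.3 about who has seen the list covers the list, not the single assignment that appears when a patient is randomized. No section masks the module display, limits the coordinator's rights in it, or stops a coordinator who randomized a patient from collecting that patient's data. The taped syringes (5.4) and uniform EMR entries (5.6) do not close this route. Section 9.2 adds little, since keeping source documents does not require knowing the arm.

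**Step 2. The plan's own figures, for scale**

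Section 3.2 gives 50 per group for 80% power. With effect size 0.66 and alpha 0.0167 (7.1), taken as two-sided because the plan does not state sidedness, the t-test needs 49.5, so 50 per group; power at 50 is 80.5%. The figure reproduces. With SD 3 (7.1), the standard error of the difference is

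SE = 3 × √(2/50) = 0.60.

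This treats SD 3 as the SD of a patient's 72-hour mean.

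**Step 3. Size of the bias under assumptions**

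Bias = w × p × s × k, where:

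- w is the weight of home scores in the 72-hour mean. If discharge is at 24 hours (assumed), there are 24/4 = 6 inpatient readings and 2 × 2 = 4 home readings, so w = 4/10 = 0.40 by count, or 48/72 = 0.67 by time.
- p is the share of home scores that the coordinator collects: 0.20 to 0.40, assumed.
- s is the shift in the arm difference on scores collected by someone who knows the arm: 0.5 to 1.0 point, assumed.
- k is the proportion of those patients whose arm the coordinator knows. It is not given, so it is varied below.

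If every arm is known (k = 1):

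- low: 0.40 × 0.20 × 0.5 = 0.04 points
- high: 0.67 × 0.40 × 1.0 = 0.27 points

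Two-sided type I error = P(Z > z − bias/SE) + P(Z < −z − bias/SE), with z = 1.96 at nominal 5%.

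| k | Bias (points) | Bias/SE | Type I error, nominal 5% |
|---|---|---|---|
| 1, low | 0.04 | 0.067 | 5.05% |
| 1, high | 0.27 | 0.45 | 6.55% + 0.80% = 7.35% |
| 0.25, high | 0.067 | 0.11 | 5.14% |
| 0.10, low | 0.004 | 0.007 | 5.00% |
| 0.10, high | 0.027 | 0.045 | 5.02% |

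At the alpha of 0.0167 in 7.1, the largest bias (0.27) gives 2.8%.

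**The case against.** The strongest reply is that access is not knowledge. Pharmacy is the primary randomizer, the schedule footnote names pharmacy alone, and only the statistician has seen the list. If pharmacy randomizes everyone and the coordinator never opens an allocation record, 5.6 holds. This stands. A reader might infer that 5.3, 5.6 and 6.5 cannot all be true; the documents do not support that. They show an unguarded route, not a certain breach.

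A reader might also infer that the outcomes are generally taken by interview. They are not. Home pain scores and 72-hour satisfaction come by e-mailed survey, opioid use to 72 hours by survey or diary, and 3-week opioid use by counting remaining pills. Direct collection is a fallback for non-compliant patients, and encouraging them to finish the survey is the alternative. Nor does 6.5 say that missed scores are collected by telephone: it speaks of contact, and specifies calls only to remind diary patients, who write their own entries. Patients are blinded, which limits a collector's influence but does not remove it.

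Finally, the 7.4% figure could be read as the expected error rate. It is the extreme of the scenarios, and requires the coordinator to know the arm for every score they retrieve. Even 0.27 points is small beside the 2-point MCID in 7.1.

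The objections narrow the exposure and the size. They supply no safeguard: nothing in the plan prevents the coordinator from randomizing a patient and then collecting that patient's missed scores.

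**Conclusion.** The point holds as an inconsistency that leaves an avoidable route to unblinded outcome collection. The exposure is confined to missed home scores of patients whose assignment the coordinator knows.

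The bias cannot be computed from the documents, because they give neither the share of scores retrieved nor how often the coordinator would randomize. The range of 0.04 to 0.27 points, with type I error from about 5.05% to 7.4%, rests on the assumptions in the working and on knowledge of every arm. It shrinks in proportion to the share of arms known. The conclusion rests on the conflict between sections and not on these figures. The change is worth making because it is cheap and the affected data enter the primary outcome.

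**What to change.** 1. In 5.3, remove the study coordinator from the randomization module and keep back-up randomization within the pharmacy team, which 5.6 already declares unblinded. This also agrees with the schedule footnote.
2. Set REDCap user rights so that nobody who contacts patients or enters outcomes can see the allocation field.
3. For any patient the coordinator has already randomized, have another existing blinded team member collect missed scores.

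The cost is a short edit to 5.3, a user-rights change and one back-up randomizer fewer. The documents do not give pharmacy staffing, so the sponsor should confirm that the pharmacy team can cover the back-up duty.

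The statistician's module access and sight of the list also conflict with 5.6, which lists statisticians as blinded. That is a separate point to reconcile; removing the coordinator does not settle it.
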